5.2.7. Statistical methodology

Categorical variables will be described by their absolute and relative frequencies. Continuous variables will be described using the mean and 95% confidence interval (95% CI), standard deviation, median, 25th and 75th percentiles, minimum and maximum, including the total number of valid values.

For the comparisons between visits for quantitative variables, parametric tests (Student's paired t-test) or non-parametric tests (Wilcoxon signed-rank test) shall be used, according to the characteristics of the variables in question.

A level

of statistical significance of 0.05 will be applied in all the statistical tests.

The data will be statistically analysed using the SAS statistical package, version 9.4 or later.

Due to the nature of this non-interventional study, there is no (confirmatory) hypothesis testing foreseen in a strict statistical sense. Analyses are descriptive in nature and confidence intervals and p-values from statistical models are used for exploratory purposes.

5.2.8. Data processing

The statistical analysis will be performed on the available data from assessable patients.

Missing data or lost values will not be imputed so as not to introduce information bias. We hope to avoid having missing data for important variables by controlling with filters when collecting data from the eCRF. Missing data on secondary endpoints, or those of lesser importance, will not affect the sample size or the outcome of the primary objective. For categorical variables, percentages will be calculated taking into account the data available, and for quantitative variables the "valid N" will be shown.

Where quantitative variables are transformed to meet normality criteria in those multivariate models requiring it, the results will be shown using the original scale. Quantitative or qualitative data may be re-codified if required for analysis.

6. RESULTS

6.1. STUDY POPULATION

6.1.1. Recruited and assessable patients

In accordance with the study protocol, we plan to enrol approximately 1087 patients to participate in the study, thanks to the cooperation of physicians at 200 cardiology or non-specialist centres in four autonomous communities in Spain.

The following table will describe the total number of assessable patients and the exclusion/inclusion criteria according to which others will be classified as non-assessable.

The following criteria will be verified:

- Inclusion criterion 1. Granting informed consent in writing prior to enrolment *Patients for whom we do not have a date of signature of the informed consent or for whom this is after the date of enrolment in the study will be excluded.*
- Inclusion criterion 2. Patients of both sexes ≥ 18 years of age with a diagnosis of NVAF. *Patients less than 18 years of age or whose age is not stated will be excluded. The diagnosis of NVAF is not assessable based on the data reported in the eCRF.*
- Inclusion criterion 3. Patients treated continuously with VKAs for stroke prophylaxis for at least six months prior to the baseline visit. *Patients for whom we do not have dates for the start and end of treatment with VKAs (month and year as a minimum) or patients who have not been undergoing treatment for at least six months will be excluded.*
- Inclusion criterion 4. Patients switching to treatment with Pradaxa® in accordance with the recommendations of the competent health authorities described in the therapeutic positioning report for NOACs and the authorisations of the various autonomous communities. *Follow-up of the recommendations of the therapeutic positioning report for NOACs is not assessable based on the data reported in the eCRF.*
- Exclusion criterion 1. Contraindications for the use of Pradaxa® or VKAs described in the Summary of Product Characteristics (SmPC). *Not assessable from data reported in the eCRF.*
- Exclusion criterion 2. Patients receiving Pradaxa® or VKAs for any reason other than stroke prophylaxis in NVAF. *Not assessable from data reported in the eCRF.*

- Exclusion criterion 3. Participation in any clinical trial of an investigational medicinal product or medical device. *Not assessable from data reported in the eCRF.*

For the criteria that are not assessable from data reported in the eCRF, patients in whom the investigator indicates criterion non-compliance in the “Selection criteria” section of the eCRF will be excluded.

[figure not shown]
Table 1. Recruited and assessable patients	
n (%)	
Patients recruited	
Non-assessable patients	
Patients who have not granted informed consent in writing prior to enrolment	
Patients under 18 years of age or not diagnosed with NVAf	
Patients who have not been treated continuously with VKAs for stroke prophylaxis for at least six months prior to the baseline visit	
Patients who were not switching to Pradaxa	
Patients receiving Pradaxa® or VKAs for any reason other than stroke prophylaxis in NVAf	
Patients with contraindications for the use of Pradaxa® or VKAs described in the Summary of Product Characteristics (SmPC)	
Patients who are participating in any clinical trial of an investigational medicinal product or medical device	
Assessable patients	
Patients for the safety sample¹	

Note: A single patient may simultaneously be classified as non-assessable for more than one reason.

¹ *All patients participating in the study with follow-up data*

The figure below is a flow diagram of study patients, which will indicate the number of recruited and assessable patients, as well as the number of patients excluded from the study.

Figure 1. Flow diagram of patients

6.2. DESCRIPTION OF THE SAMPLE AT BASELINE

6.2.1. Socio-demographic data

This section will describe the socio-demographic data of the patients in the study.

Figure 2. Distribution of the sex of patients
(Pie chart: Male/Female)

Table 2. Age of patients (years)	
	Total
Age (years)	
Mean (SD)	
95% CI	
Median (P25; P75)	
(Min; Max)	
Valid N	
Age in categories	
≤65 years	
>65 years	

Figure 3. Distribution of patient ages
(Pie chart: ≤ 65 years / > 65 years)

Table 3. Description of race	
	n (%)
Race	
Caucasian	
North African	
Sub-Saharan African	
Afro-American	
Latin American	
Asian	
Other	
...	

Figure 4. Distribution of patients by AC
 (Map: Catalonia/Galicia/Andalusia/Basque Country)

6.2.2. Anthropometric data and vital signs

This section will describe the data related to anthropometric characteristics and vital signs at the time of the baseline visit.

Table 4. Anthropometric characteristics	
	Total
Weight (kg)	
Mean (SD)	
95% CI	
Median (P25; P75)	
(Min; Max)	
Valid N	
Height (cm)	
Mean (SD)	
95% CI	
Median (P25; P75)	
(Min; Max)	
Valid N	
BMI (kg/m²)	
Mean (SD)	
95% CI	
Median (P25; P75)	
(Min; Max)	
Valid N	

Table 5. Vital signs	
Total	
Heart rate (bpm)	
Mean (SD)	
95% CI	
Median (P25; P75)	
(Min; Max)	
Valid N	
Systolic blood pressure (mmHg)	
Mean (SD)	
95% CI	
Median (P25; P75)	
(Min; Max)	
Valid N	
Diastolic blood pressure (mmHg)	
Mean (SD)	
95% CI	
Median (P25; P75)	
(Min; Max)	
Valid N	

6.2.3. Medical history

This section will describe the medical history data of the patients participating in the study.

Table 6. Clinically relevant disease and/or surgery			
	n	%¹	%²
Clinically relevant disease and/or surgery			
Yes			--
No			--
Type of disease and/or surgery			
Ischaemic stroke			
Episodes of bleeding, anaemia or predisposition to bleeding			
Arterial thromboembolisms outside of the CNS			
Diabetes mellitus			
Hypertension			
Hyperlipidaemia			

Table 6. Clinically relevant disease and/or surgery

	n	% ¹	% ²
Stable angina pectoris			
Acute Coronary Syndrome. ST-segment elevation myocardial infarction (ACS-STEMI)			
Acute Coronary Syndrome. Non-ST-segment elevation myocardial infarction (ACS-NSTEMI)			
Acute Coronary Syndrome (ACS). Unstable angina			
Peripheral arterial disease			
Procedure performed in vascular disease (last episode) or bypass			
Congestive heart failure			
Left ventricular dysfunction			
Abdominal aortic aneurysm			
Aortic plaque			
Kidney failure (chronic dialysis, kidney transplant or creatinine \geq 2.26 mg/dl)			
Liver failure (cirrhosis or biochemical data indicative of liver impairment, bilirubin $>$ 2 x ULN, AST/ALT $>$ 3 x ULN)			
Vascular disease			
Alcoholism			
\geq 8 alcoholic drinks per week (% around n=XX)			
$<$ 8 alcoholic drinks per week (% around n=XX)			
Known unstable INR (time in therapeutic range $<$ 60% by the direct method or $<$ 65% by the Rosendaal method)			
Others			
...			
...			
...			

¹ Percentages calculated based on the total number of assessable patients (n=XX)

² Percentages calculated based on the total number of patients with a history of clinically relevant disease and/or surgery (n=XX)

Note: A single patient may simultaneously specify more than one disease and/or surgery

6.2.4. Creatinine clearance

This section will describe the serum creatinine values taken from the last blood test, as well as creatinine clearance values.

Table 7. Serum creatinine and creatinine clearance	
	Total
Serum creatinine (mg/dl)	
Mean (SD)	
95% CI	
Median (P25; P75)	
(Min; Max)	
Valid N	
Creatinine clearance (Cockcroft-Gault) (ml/min) *	
Mean (SD)	
95% CI	
Median (P25; P75)	
(Min; Max)	
Valid N	

* $Cockcroft-Gault = ((140 - age) \times Weight (kg)) / (72 \times creatinine (mg/dl)) \times 0.85$ (if female)

Patients will also be classified by disease stage based on their Cockcroft-Gault values (ml/min):

Table 8. Stages of kidney disease based on creatinine clearance	n (%)
Stages of kidney disease (based on Cockcroft-Gault)	
No kidney failure (> 80 ml/min)	
Mild kidney failure (50-80 ml/min)	
Moderate kidney failure (30-49 ml/min)	
Severe kidney failure (15-29 ml/min)	
End-stage kidney failure/dialysis (< 15 ml/min)	

6.2.5. Treatment

6.2.5.1 VKA treatment

This section will describe the data on previous anticoagulant treatment with VKAs.

Table 9. Previous VKA treatment		
	n (%)	Duration (months) Mean (SD)
		Dose (mg/day) Mean (SD)
Active substance of the VKA¹ and treatment duration		
Acenocoumarol		
Warfarin		
Others		
...		
...		

¹ A single patient may simultaneously specify more than one active substance

6.2.5.2 Pradaxa[®] treatment

This section will describe the reasons for switching from VKAs to Pradaxa[®], as well as the prescribed dose.

Table 10. Reasons for switching from VKAs to Pradaxa[®]	
	n (%)
Reason¹ triggering the switch from VKAs to Pradaxa[®]	
Hypersensitivity to the drug	
Patients with a history of intracranial haemorrhage (ICH) (except during the acute phase) in whom the benefits of anticoagulation are deemed to outweigh the risk of haemorrhage.	
Patients with ischaemic stroke who present clinical and neuroimaging criteria indicating a high risk of ICH	
Patients undergoing treatment with VKAs, suffering from severe arterial thromboembolic episodes despite good INR control.	
Patients who have started treatment with VKAs in whom it is not possible to keep the INR in range (2-3) despite good therapeutic compliance.	
Lack of access to conventional INR management	
Patient's decision	
Others	
...	
Unknown	

¹ A single patient may simultaneously specify more than one reason

Figure 5. Pradaxa[®] dose
(Pie chart: 110 mg / 150 mg)

6.2.6. Scales

6.2.6.1 HAS-BLED scale

This section will describe the scores obtained on the HAS-BLED scale and the corresponding haemorrhagic risk levels.

Riesgo hemorrágico (escala HAS-BLED)
•Puntuación = 0: bajo
•Puntuación = 1-2: intermedio
•Puntuación \geq 3: alto

Riesgo hemorrágico (escala HAS-BLED)	Haemorrhagic risk (HAS-BLED scale)
Puntuación	Score
bajo	low
intermedio	intermediate
alto	high

Table 11. HAS-BLED scale	
	n (%)
HAS-BLED scale	
Uncontrolled hypertension with SBP \geq 160 mmHg	
Kidney failure	
Liver failure	
History of stroke	
History of bleeding, anaemia or predisposition to bleeding	
Unstable/high or poor INR (<60% of time within therapeutic range)	
Age > 65 years	
Medications that affect haemostasis	
Consumptions of \geq 8 alcoholic drinks per week	

Table 12. HAS-BLED scale score and haemorrhagic risk
HAS-BLED score
Mean (SD)
95% CI
Median (P25; P75)
(Min; Max)
Valid N
Haemorrhagic risk based on the HAS-BLED scale n (%)
Low risk
Intermediate risk
High Risk

6.2.6.2 CHA₂DS₂-VASc classification

This section will describe the scores obtained on the CHA₂DS₂-VASc scale and the corresponding thromboembolic risk levels.

Riesgo tromboembólico (escala CHA₂DS₂-VASc)

 •Puntuación = 0: bajo •Puntuación = 1: intermedio •Puntuación ≥ 2: alto

Riesgo tromboembólico (escala CHA ₂ DS ₂ -VASc)	Thromboembolic risk (CHA ₂ DS ₂ -VASc scale)
Puntuación	Score
bajo	low
intermedio	intermediate
alto	high

Table 13. CHA₂DS₂-VASc scale	
	n (%)
CHA₂DS₂-VASc scale	
Congestive heart failure/left ventricular dysfunction	
Hypertension	
Age ≥ 75 years	
Diabetes mellitus	
Stroke/TIA/thromboembolism	
Vascular disease (history of myocardial infarction, peripheral artery disease or aortic plaque)	
Age 65-74 years	
Female sex	

Table 14. CHA₂DS₂-VASc scale and thromboembolic risk	
CHA₂DS₂-VASc scale score	
Mean (SD)	
95% CI	
Median (P25; P75)	
(Min; Max)	
Valid N	
Thromboembolic risk based on the CHA₂DS₂-VASc scale n (%)	
Low risk	
Intermediate risk	
High Risk	

6.2.6.3 PACT-Q2 Questionnaire at Baseline

This section will describe the items in the PACT-Q2 questionnaire and the scores obtained for the respective domains.

Table 15. PACT-Q2 Questionnaire at Baseline (I)					
CONVENIENCE	Not at all	A little bit	Moderately	A lot	A great deal
	n (%)	n (%)	n (%)	n (%)	n (%)
B1. In what way do you find it difficult to take your anticoagulant treatment (because they are pills or injections, because of the number you have to take or how often you have to take them, etc.)?					
B2. To what extent do you find it bothersome to take your anticoagulant treatment?					
B3. Do you sometimes need to adjust the dose of some anticoagulant treatments? Does this cause you any difficulties?					
B4. There are certain types of medication that CANNOT BE TAKEN while you are on anticoagulant treatment. Does this cause you any difficulties?					
B5. You are advised to avoid certain foods while on anticoagulant treatment. Does this cause you any difficulties?					
B6. To what extent do you find it difficult to take your anticoagulant treatment when you are not at home?					
B7. To what extent do you find it difficult to organise your time around your anticoagulant treatment (appointments with nurses, doctors, laboratories, etc.)?					
B8. To what extent do you find the medical follow-up required for your anticoagulant treatment bothersome?					
B9. To what extent do you find it difficult to take the anticoagulant treatment regularly following your doctor's instructions?					
B10. Do you feel that you are more dependent on others (your partner,					

Table 15. PACT-Q2 Questionnaire at Baseline (I)					
CONVENIENCE	Not at all	A little bit	Moderately	A lot	A great deal
	n (%)	n (%)	n (%)	n (%)	n (%)
family, nurse, etc.) due to your anticoagulant treatment?					
B11. To what extent does having to interrupt or discontinue your anticoagulant treatment worry you?					
C1. Are your day-to-day activities (work, leisure, social events, physical activities, etc.) limited due to the potential side effects of the treatment (small bruises, bleeding, etc.)?					
C2. How much physical discomfort do the bruises or pain cause?					

Table 16. PACT-Q2 Questionnaire at Baseline (II)					
SATISFACTION WITH THE ANTICOAGULANT TREATMENT	n (%)	n (%)	n (%)	n (%)	n (%)
	Not at all	A little bit	To some extent/moderately	A lot	Completely
D1. To what extent do you feel more at ease thanks to your anticoagulant treatment?					
D2. Do you think that the anticoagulant treatment you are taking has been able to reduce your symptoms (pain or swelling in the legs, palpitations, shortness of breath, chest pain, etc.)?					
	They are much worse than I expected	They are worse than I expected	They are about what I expected	They are better than I expected	They are much better than I expected
D3. How do the side effects you have, such as small bruises or bleeding (when shaving, cooking, if you cut yourself, etc.) compare to what you expected?					

Table 16. PACT-Q2 Questionnaire at Baseline (II)

SATISFACTION WITH THE ANTICOAGULANT TREATMENT	n (%)	n (%)	n (%)	n (%)	n (%)
	Very unsatisfactory	Unsatisfactory	Neither satisfactory nor unsatisfactory	Satisfactory	Very satisfactory
D4. With regard to the follow-up of your disease and the anticoagulant treatment you are taking, what is your degree of satisfaction with your level of independence?					
D5. What is your degree of satisfaction with the methods (appointments with nurses, doctors, laboratories, etc.) used to ensure the follow-up of your disease and anticoagulant treatment?					
D6. What is your degree of satisfaction with the presentation of your anticoagulant treatment (pill to be taken orally/injections)?					
D7. In general, what is your degree of satisfactions with your anticoagulant treatment?					

The PACT-Q2 questionnaire is made up of two domains:

- Convenience (items B1 to B7 and C1 to C2) → This domain is calculated by adding the inverted scores (6 – item score) for each of the 9 items in question, and converting to a scale from 0 to 100.
- Satisfaction with the anticoagulant treatment (items D1 to D7) → This domain is calculated by adding the scores for each of the 7 items in question, and converting to a scale from 0 to 100.

The table below will describe the scores obtained for both domains:

Table 17. PACT-Q2 Questionnaire Score at Baseline¹
DOMAINS
Convenience Mean (SD) 95% CI Median (P25; P75) (Min; Max) Valid N
Satisfaction with the anticoagulant treatment Mean (SD) 95% CI Median (P25; P75) (Min; Max) Valid N

¹ Range from 0 to 100

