6.3.2. Scales

6.3.2.1 PACT-Q2 Questionnaire at Follow-up

This section will describe the items in the PACT-Q2 questionnaire and the scores obtained for the respective domains for each follow-up visit.

VISIT 2

Table 20. PACT-Q2 questionnaire - VISIT 2 (I)						
CONVENIENCE		Not at all	A little bit	Moderately	A lot	A great deal
		n (%)	n (%)	n (%)	n (%)	n (%)
B1. In what way do you find it difficult to take your anticoagulant treatment (because they are pills or injections, because of the number you have to take or how often you have to take them, etc.)?						
B2. To what extent do you find it bothersome to take your anticoagulant treatment?						
B3. Do you sometimes need to adjust the dose of some anticoagulant treatments? Does this cause you any difficulties?						
B4. There are certain types of medication that CANNOT BE TAKEN while you are on anticoagulant treatment. Does this cause you any difficulties?						
B5. You are advised to avoid certain foods while on anticoagulant treatment. Does this cause you any difficulties?						
B6. To what extent do you find it difficult to take your anticoagulant treatment when you are not at home?						
B7. To what extent do you find it difficult to organise your time around your anticoagulant treatment (appointments with nurses, doctors, laboratories, etc.)?						
B8. To what extent do you find the medical follow-up required for your anticoagulant treatment bothersome?						
B9. To what extent do you find it difficult to take the anticoagulant						

Table 20. PACT-Q2 questionnaire - VISIT 2 (I)					
CONVENIENCE	Not at all	A little bit	Moderately	A lot	A great deal
	n (%)	n (%)	n (%)	n (%)	n (%)
treatment regularly following your doctor's instructions?					
B10. Do you feel that you are more dependent on others (your partner, family, nurse, etc.) due to your anticoagulant treatment?					
B11. To what extent does having to interrupt or discontinue your anticoagulant treatment worry you?					
C1. Are your day-to-day activities (work, leisure, social events, physical activities, etc.) limited due to the potential side effects of the treatment (small bruises, bleeding, etc.)?					
C2. How much physical discomfort do the bruises or pain cause?					

Table 21. PACT-Q2 questionnaire - VISIT 2 (II)					
SATISFACTION WITH THE ANTICOAGULANT TREATMENT	n (%)	n (%)	n (%)	n (%)	n (%)
	Not at all	A little bit	To some extent/moderately	A lot	Completely

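### The SAP lists 13 items under Convenience but scores 9 of them; B8 to B11 enter no score, and no reason is given

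*SAP*

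**What the plan says.** Section 6.2.6.3 of the SAP states that "The PACT-Q2 questionnaire is made up of two domains". It builds the first from "Convenience (items B1 to B7 and C1 to C2"), adding the inverted scores (6 minus the item score) "for each of the 9 items in question, and converting to a scale from 0 to 100". The second, Satisfaction, takes D1 to D7, summed "for each of the 7 items in question, and converting to a scale from 0 to 100". The footnote to Table 17 gives the result as "Range from 0 to 100".

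The item tables are laid out differently. Table 15 (baseline), Table 20 (Visit 2) and Table 22 (Visit 3) each list B1 to B11 and C1 to C2 under the single heading of Convenience. They include, for example, "B8. To what extent do you find the medical follow-up required for your anticoagulant treatment bothersome" and "B11. To what extent does having to interrupt or discontinue your anticoagulant treatment worry you".

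The section opens by announcing two kinds of output: "This section will describe the items in the PACT-Q2 questionnaire and the scores obtained for the respective domains". Nothing in the SAP says that B8 to B11 are meant to be reported without being scored.

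**The concern.** Convenience is one of the two scores compared between visits in the primary analysis (sections 5.2.3 and 6.4.1, Table 25), and treatment convenience is the subject of the study title. The scoring rule feeds Tables 17, 24 and 25 and Figure 6.

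If the item tables show the true domain, the rule as written drops four of its items: how bothersome medical follow-up is (B8), difficulty in taking the treatment as instructed (B9), dependence on others (B10) and worry about interruption (B11). The dividing line is not self-evident either. B7, on organising time around appointments, is scored, while B8, on the bother of follow-up, is not.

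If the rule is right, a reader of Tables 15, 20 and 22 will take B8 to B11 to be part of a score that does not contain them. In both cases the SAP leaves open what the primary Convenience score is supposed to measure.

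**Working it through.** **Step 1: the rule's own count.** B1 to B7 is 7 items and C1 to C2 is 2, so 7 + 2 = 9. This agrees with the count written in section 6.2.6.3, so the rule is consistent in itself.

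**Step 2: rule against tables.**

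| Domain | Listed in the item tables | Scored by the rule | Unscored |
|---|---|---|---|
| Convenience | B1-B11, C1-C2 = 11 + 2 = 13 | 9 | B8-B11 = 4 |
| Satisfaction | D1-D7 = 7 | 7 | 0 |
| Total | 20 | 16 | 4 |

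The unscored share of Convenience is 4/13 = 31%. The SAP names only two domains and Satisfaction is confined to D1 to D7, so there is no other score to which B8 to B11 could belong. The 13-item layout appears in three separate tables, and the nine-item range agrees with its written count. A fault in reading the PDF is therefore not a plausible explanation.

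**Step 3: what the choice could mean on the 0-100 scale.** Five response columns and inversion as 6 minus the item score imply coding from 1 to 5. The SAP does not write out the conversion, so I assume a linear one and complete responses.

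- Nine items: the inverted sum runs from 9 to 45 (span 36), so score = (sum - 9)/36 x 100. One category on one item is worth 100/36 = 2.78 points.
- Thirteen items: the inverted sum runs from 13 to 65 (span 52), so score = (sum - 13)/52 x 100. One category on one item is worth 100/52 = 1.92 points.

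Let m9 be the mean improvement in categories on the nine scored items, and m4 that on B8 to B11.

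- 9-item change = 100/36 x 9 x m9 = 25 x m9
- 13-item change = 100/52 x (9 x m9 + 4 x m4) = 25 x (9 x m9 + 4 x m4)/13
- Difference (13-item minus 9-item) = 25 x 4/13 x (m4 - m9) = 7.69 x (m4 - m9)

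| Gap m4 - m9 (categories, assumed) | Difference in change (points) |
|---|---|
| 0 | 0 |
| 0.25 | 1.9 |
| 0.5 | 3.8 |
| 1 | 7.7 |

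A negative gap gives the same size with the opposite sign.

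**Step 4: bound for a single score.** With the nine items at their best category and B8 to B11 at their worst, the 9-item score is 100 and the 13-item score is 36/52 x 100 = 69.2. In the reverse case they are 0 and 16/52 x 100 = 30.8. One patient's two scores at one visit can thus differ by at most 30.8 points. If the two item groups have the same mean, they do not differ at all.

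**Step 5: sample size.** Section 4.2 uses a standardised difference of 0.11, 90% power and two-sided alpha of 0.05. This gives (1.960 + 1.282)²/0.11² = 868.4, rounded up to 869, and 869/0.8 rounds up to 1087. The plan's figure reproduces. The number of items does not enter this calculation, so N is unaffected.

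**The case against.** The strongest reply is that the score is already defined. The range and the written count independently give nine, there is no competing scoring rule, and a programmer would know what to do. The item tables are frequency shells, and section 6.2.6.3 announces items and domain scores as separate outputs, so an item may be tabulated without being scored. The reason for an instrument's item selection often sits in the protocol or in the scoring instructions, neither of which is at hand. The same rule applies at every visit, so paired comparisons stay coherent; B8 to B11 are still reported item by item; and section 5.2.7 calls the analyses descriptive and the p-values exploratory. The size of any effect is hypothetical.

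Most of this stands as a limit on the point. It does not show that a nine-item score is wrong, and it does not remove the conflict. The SAP itself places B8 to B11 under the Convenience heading, says there are only two domains, and leaves these four items out of both without comment, while the other domain matches its table exactly. Consistent use across visits does not settle whether the score covers the domain that the tables label. Nor does item-level reporting make up for it: the tables give only marginal frequencies at each visit, from which the paired change and the test for a 13-item score cannot be rebuilt.

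**Conclusion.** The point holds. The Convenience rule conflicts with the SAP's own item tables: 13 items are listed, nine are scored, and four (31%) enter no score, without a stated reason. It concerns one of the two primary-endpoint scores at all three visits, so it should be settled before scores are computed.

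The mismatch is certain; a scoring error is not, because the SAP alone does not show whether the rule or the table heading is at fault. The effect on the mean change cannot be derived from the document. The 7.7 points per category of gap and the 30.8-point bound rest on 1-5 coding, a linear conversion and complete responses, and the gaps in the table are illustrations. I claim no direction of bias and no loss of power.

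**What to change.** Before scoring, check section 6.2.6.3 against the questionnaire's scoring instructions and cite them in the SAP. Then take one of two routes.

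- **If the instructions score all 13 items:** change the rule to B1 to B11 and C1 to C2, 13 items, with score = (sum of inverted scores - 13)/52 x 100, and produce Tables 17, 24 and 25 and Figure 6 from it.
- **If they score nine items:** keep the rule, add a sentence saying why B8 to B11 are left out, and relabel Tables 15, 20 and 22 so that these items are not shown as part of the scored domain.

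The cost is one check, followed by either one line of SAP text and one line of SAS code, or one sentence and new labels in three tables. No new data are needed, because the item tables provide for B8 to B11 at all three visits.
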